Despite this growing literature, there is a gap in the published research regarding opioid use disorder and comorbid PTSD.[28] There is some evidence that treatment with buprenorphine among those with PTSD leads to an overall improvement in treatment outcomes[28] and an observational study suggests buprenorphine treatment is associated with improvement in PTSD symptoms compared to a control group prescribed high dose opioid therapy.[66] Despite these advances, there are no studies evaluating the combination of opioid substitution therapy with a PTSD evidence-based treatment. This has been identified as an important area of study[28] that the proposed research is intended to address.

Studying an evidence based psychotherapy for co-occurring PTSD among those with comorbid OUD has substantial significance and great clinical relevance. To apply an intervention to a new vulnerable clinical population has a potential to change clinical practice. Most importantly, this study has the potential to fill knowledge gaps and challenge the VA to improve healthcare delivery based on scientific evidence.

We would like to underscore that while we hypothesize that CPT will be safe and effective for Veterans with PTSD and OUD, we believe that we cannot assume this to be true. There is a body of literature that suggests that treatments developed for a single condition, such as PTSD, are not equally effective when used in individuals with comorbidity. For example, medications to treat PTSD including the FDA-approved antidepressant, sertraline and the alpha adrenergic medication prazosin [which are recommended by the VA/DoD practice guidelines [67] for sleep disturbances associated with PTSD] are *not equally effective* when used among individuals with comorbid alcohol use disorders.[68-71] Without well-designed clinical trials conducted in comorbid groups, assumptions about efficacy would have been mistaken. *Particularly with behavioral therapies*, there is controversy regarding the use of evidence-based psychotherapy in individuals with comorbid substance use disorders for fear of precipitating relapse.[62] Studies among those with opioid use disorders maintained on buprenorphine are therefore important. *Clinical trials are needed to show efficacy and safety.*

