6. RESEARCH PLAN

Research design and methods

Overview: We propose to conduct a randomized, controlled trial with 160 (assuming a 30% drop out rate, for 120 participants) Veterans and civilians diagnosed with PTSD and comorbid OUD. This study will use *open*

randomization to 2 groups: (a) buprenorphine + CPT vs. (b) *buprenorphine + IDC*. All subjects will be maintained on buprenorphine and the standard clinical treatment. Participants will be recruited primarily through the clinical facilities at the VA and from other collaborators.

The Bedford VAMC has been added as an additional enrollment site for this study. The principal investigator for the Bedford site is [name] and the study will be overseen by the Bedford VA IRB has gained local IRB approval.

Experimental subjects: Veterans and civilians (n=160) aged 18- 65 years old, with a current diagnosis of PTSD and opioid use disorder (OUD) will be enrolled at 2 sites (VA Connecticut Healthcare System, Bedford VAMC) for a study with 12-weeks of active treatment. Participants will be recruited from four main sources: 1) from the PTSD clinic patients at the local VAs , 2) from the group of Veterans entering treatment for opioid use disorders at the local VA Substance Abuse Treatment Programs and 3) advertisement (flyers, posters, Craigslist) 4. Community clinics. Under a HIPAA waiver, IRB-approved letters of invitation can be mailed to prospective participants with a past diagnosis of OUD or PTSD who otherwise might meet eligibility criteria. Outreach will also be conducted at local Veteran Centers, where staff from both VAs consult. The PTSD staff has also been involved in outreach to the community for returning OIF/OEF Veterans. Each participant will be carefully screened and assessed using the following inclusion and exclusion criteria:

Inclusion Criteria:

- 1) Male and female Veterans and civilians between the ages of 18-70 years old.
- 2) Current diagnosis of PTSD as determined by an independent evaluator assessment using CAPS-5.
- 3) Opioid Use Disorder diagnosed by Mini International Neuropsychiatric Interview for DSM-5 (MINI). To meet entry criteria for buprenorphine treatment, will also have documented prior treatment for opioid use disorder, history of opioid withdrawal or signs of opiate withdrawal as evidenced by a Clinical Opiate Withdrawal Scale (COWS) score of 7 or greater, and a positive urine toxicology for opioids.

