- 4) For women, negative pregnancy test and use of acceptable method of contraception.

Please note, because of the high incidence of depression that co-occurs with PTSD, those individuals with comorbid depressive disorders will be allowed into the study. This is in keeping with the purpose of this study to evaluate the effectiveness of a CPT in a “real world” clinical population. It also is anticipated that a significant proportion of Veterans and civilians will likely be treated with concurrent antidepressant pharmacotherapy [and/or with other medications (eg. prazosin).] However, again this enhances the “real world” application of treatments within the VA system, and secondly it is common to allow antidepressant medication in psychotherapy trials and still be able to show benefit with CPT.[37] For those who are already prescribed antidepressant medication, they will be continued on their current pharmacologic treatment Please note that since not all subjects will be on psychotropic medications, randomization will be stratified by presence of concurrent medications-a strategy we have used successfully in other comorbidity studies with PTSD[71]

Exclusion Criteria:

- 1) Females who are pregnant or lactating.
- 2) Veterans and civilians with a current unstable medical condition such as neurological, cardiovascular, endocrine, renal, liver, or thyroid pathology (e.g. abnormal BUN and creatinine, and unmanaged hypertension with BP > 200/120) which in the opinion of the physician would preclude the patient from fully cooperating or be of potential harm during the course of the study.
- 3) Veterans and civilians who meet current criteria for the following diagnoses (schizophrenia and schizophrenia spectrum and psychotic disorders) as determined by the MINI.
- 4) Veterans and civilians who have significant current suicidal or homicidal risks necessitating a higher level of care.
- 5) Those with known allergy or intolerance to buprenorphine.

Methods:

Overview: This study is a 14-week, RCT with open-label randomization to 2 groups (described in detail below): (a) buprenorphine (BUP) + CPT vs. (b) BUP + IDC. This study will be conducted in 3 Phases: Phase I:

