buprenorphine induction and stabilization for all participants (x1 week). Participants will be started at a dose of 2mg/0.5 mg BUP/NLX and this dose will be increased as needed for stabilization of opioid withdrawal symptoms up to 32 mg per day, which is standard practice. Phase II: randomization to CPT vs. IDC (x12 weeks). *CPT will be provided by one of our licensed therapists trained and who has been trained and certified in the standard VA rollout. The therapists will have weekly case consultation from a qualified CPT consultant. IDC will be provided by research staff under the supervision of [name]. All of the sessions will be recorded for supervision purposes and for the independent fidelity raters to assess 20% of the sessions for adherence and competence.** [Phase III: Subjects will be referred to one of the buprenorphine clinics (West Haven or Newington) and will be referred for ongoing treatment for PTSD if they choose, including the option for CPT for those who did not receive this during the study.]

Participants will be seen on a daily basis (excluding weekends) for the initial 5-7 day induction. Once subjects are on maintenance dose of BUP/NLX (goal is within 5 days), they will be seen weekly by study RN for the first 4 weeks, biweekly for a month then monthly for symptom evaluation, and medication refill.

[At study end, participants will be referred to a buprenorphine clinic. *Buprenorphine treatment is the standard treatment for OUD, and subjects who discontinue are at high risk for relapse.*]

* Due to COVID-19 precautions it may not be possible to record CPT/IDC sessions especially those conducted via telephone or telemedicine.

Main Outcome Measures: Symptoms of PTSD using the CAPS-5 and PCL-5. Frequency of opioid use using the TLFB and confirmed by urine toxicology. Other outcomes will include treatment retention measured by days in treatment and functioning using the VR-12. Functional impairment related to pain will be measured during the trial. Follow-up will be conducted at 1 and 3 months after end of the study to evaluate the durability of treatment effects on drug use and psychosocial outcomes.

To fully assess and appreciate complex symptomatology in this patient population, assessments were selected to have both relevance to our study of PTSD and comorbid OUD. Assessments will be done by an Independent Evaluator (IE) blind to treatment group.

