+ *Subjects will be allowed to receive their medications according to their clinic dosing schedule (weekly, monthly, daily) and can change based on the clinical judgement of the provider.*

Any participants already taking Buprenorphine will skip the induction phase and continue with their prescribed dose dispensed through the research pharmacy while enrolled in this study. For participants receiving daily Buprenorphine through the Methadone clinic, they will continue to receive their medication from there. Any participants who cannot tolerate BUP/NLX and are on standalone Buprenorphine will continue to receive their medication directly from their VA provider.

Buprenorphine is a Schedule III drug that, in community settings, is often prescribed for up to a one month's supply at a time. Patients are generally seen on a weekly or monthly basis like those treated with other psychiatric medications. Buprenorphine will be delivered by the research pharmacy on the day of the participant's weekly, biweekly, or monthly appointment, and will be returned to the research pharmacy should the subject fail to present for the appointment. Buprenorphine treatment is generally well tolerated. Its side effects, such as abdominal pain, constipation, nausea, vomiting, headache and sweating, are similar to other opioids. Increases in liver enzymes and hepatitis are rarely reported. Participants will be educated to keep their medication in a safe place to prevent unintentional exposure to others, especially children.

Medical Management: Medical Management (MM) will be provided for all patients in the study. It is a behavioral intervention designed for patients with substance dependence, and is particularly well suited to a medication clinical trial [76]. The objective of MM is to focus on medication compliance and symptom reduction. In this study MM will be provided by a trained registered nurse and will be conducted at each visit. The initial visit will be 40-60 minutes and the focus will be on educating the patient on medication regimen and compliance; other health issue such as negative consequences of drug use, may also be discussed. Consecutive sessions will be 15-20 minutes and will be focused on monitoring of compliance with the medication and psychoeducation. This intervention was chosen because of MM's focus on medical issues which

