Subject Payment. All participants will be compensated for their participation. Participants will be paid \$30 for the initial screening/baseline assessment. They will be compensated \$30 for each medication visit (x7), and \$45 for follow up visits. There will be no payment for therapy sessions. Individuals can receive up to a total of \$330 if attending all scheduled treatment and visits. Payment will be made through electronic funds transfer (EFT). Participants will need to provide us with your banking information by completing a special payment form. Alternatively, if participants do not have a bank account, a check will be mailed to them instead. This check(s) will be mailed to the address they provide us with. Patients may choose to receive gift certificates issued to them for use at the VCS canteen (retail store) or VCS cafeteria here at the VACHS in lieu of EFT/check payment. If a patient chooses to receive payment by gift certificate they will be paid for the telemedicine/telehealth visits they participated in at their next in-person visit (e.g. if they complete weeks 2 and 3 by telephone they will receive gift certificates for weeks 2, 3, and 4 at the week 4 visit). Study payments are subject to withholding for outstanding federal debts (i.e., defaulted student loans, interstate child support, back taxes etc) without notification.

Power analysis: The sample size calculation for our primary hypothesis (change in PTSD symptoms) was based on findings from one of the largest and most comprehensive meta-analysis reports on PTSD treatment to date.[36] The report evaluated N=112 studies and reported on 137 comparisons, using validated PTSD symptom measures. The meta-analysis reported that the *effect sizes* for psychotherapy when contrasted with a control group were consistently large and averaged $g=1.14$. Three studies administered CPT specifically and the overall effect size for those was large and averaged $g=1.69$. For this study we conservatively are basing our calculations on a moderate effect size by Cohen's definition.[95] For the First and Second Primary aim we estimate that with 60 subjects randomized to each group we have 80% power to detect a medium effect size ($f=0.25$) at two-sided alpha level of 0.05, and assuming 25% dropout we will recruit a total of N=160.]

Data Analysis:

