c) Subjects who are randomized to Individual Drug Counseling (IDC) will receive 12 weeks of therapy by a licensed provider. IDC uses a semi-structured, time-limited addictions-counseling model. The main focus is on helping individuals achieve and maintain abstinence by encouraging behavioral changes, such as avoiding triggers, structuring one's life, and engaging in healthy behaviors (e.g., exercise). The current standard of treatment for individuals entering buprenorphine maintenance is to do drug counseling. In most VA settings, including VA Connecticut Healthcare System, psychiatric symptoms (such as PTSD) are evaluated but psychiatric treatment is often deferred until the individual demonstrates a commitment to treatment and demonstrates abstinence. Standard counseling is the primary means to achieve these goals. PTSD symptoms are not addressed and this may lead to worsening of PTSD symptoms. In cases where worsening of PTSD symptoms necessitates a change in case, the same strategies (outlined later in this document) will be used across treatment conditions.

d) Nonspecific Risks: Other risks from the counseling, rating scales and urine collections are not beyond usual clinical procedures in a substance abuse treatment program. Confidentiality of study results are specifically protected by Federal laws, and all records will be identified by code number only, with the master file kept under lock by the Principal Investigator or Data Manager. With the handling of medical and research records, there is always the possibility of a breach of confidentiality.

- **Sources of Materials:** Sources of research material include interview assessments conducted by trained Independent Evaluators, self-reported questionnaires, medical record review, urine samples, activity patterns, sleep patterns, etc. that will be obtained specifically for research purposes.
- **Therapeutic risk:** All subjects will be inducted into buprenorphine maintenance, the risks of which are described above.
- **Research risk:** The research risks include the risks of the interventions into which subjects will be randomized, and include CPT and standard counseling, all of which are described above. In addition, there are risks associated with gathering of assessments, and a potential breach of confidentiality. These have also been described above.

Adequacy of Protection from Risk

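### Buprenorphine status at entry (new induction or already taking it) is neither a randomisation stratum nor a prespecified covariate, which costs precision and leaves Secondary Aim 1 harder to interpret

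*Combined protocol and SAP*

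**What the plan says.** **Who enters.** Section 6, Standard Treatment for all Participants, provides: "Any participants already taking Buprenorphine will skip the induction phase and continue with their prescribed dose". The Recruitment and Informed Consent paragraph adds that charts of Buprenorphine Clinic patients are screened for candidates, so this is a planned source of recruits. Other parts describe a trial in which nobody skips induction. The Methods overview makes a one-week induction Phase I for every participant, the Standard Treatment section describes an induction start for all, and Potential Risks states: "All subjects will be inducted into buprenorphine maintenance".

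**Opioid use at entry.** Inclusion criterion 3 lists documented prior treatment, a history of withdrawal or current withdrawal signs, "and a positive urine toxicology for opioids". It introduces these as what is needed to start buprenorphine treatment. It does not say whether they bind someone already on it. Baseline opioid use comes from the Timeline Follow-back (TLFB) for the preceding month.

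**Allocation and analysis.** In the note under the inclusion criteria, "randomization will be stratified by presence of concurrent medications", which in context means psychotropic medication. The models under Primary and Secondary Hypotheses contain treatment and time, and the hypothesis is tested by their interaction. The Data Analysis section compares the arms at baseline and makes covariates of variables that differ. Its examples include opiate use but not buprenorphine status.

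**The concern.** The protocol itself gives reasons to expect different courses. Section C (Significance) says that opioid withdrawal can bring on or imitate PTSD symptoms, and that "an observational study suggests buprenorphine treatment is associated with improvement in PTSD symptoms". New inductees go through that change during the trial, in both arms; patients already taking buprenorphine have at least partly been through it. For retention, the chart review in section D(4) shows 10/10, 11/36 and 28/53 new admissions retained at three months, together 49 of 99. A patient maintained for longer than that has already passed the period in which about half of new admissions were lost.

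A factor of this kind, known at consent and left out of both allocation and model, adds residual variance to the PTSD, opioid-use and retention comparisons and can be unevenly split by chance. There is a further issue for Secondary Aim 1. If the positive-urine rule does not bind maintained patients, some of them may have little opioid use left to reduce. A null result would then be hard to interpret without results by status.

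**Working it through.** **1. The plan's own figure.** The Power analysis claims "with 60 subjects randomized to each group we have 80% power to detect a medium effect size". It gives that effect as f=0.25, tests two-sided at 5%, and reaches its total of 160 by allowing for a quarter of patients dropping out. For two equal groups d = 2f = 0.5. Normal approximation: 0.5 × √(60/2) = 2.739; 2.739 − 1.960 = 0.779; power 78% (77.5% by noncentral t). Recruitment: 120/(1 − 0.25) = 160. The plan's figures reproduce to within about 2 points.

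**2. Chance imbalance.** The documents give no share of patients already taking buprenorphine, so I vary it. Exact binomial probability that the arms differ by 10 percentage points or more:

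| Assumed share already taking | 80 per arm | 60 per arm |
|---|---|---|
| 20% | 14% | 21% |
| 35% | 21% | 29% |
| 50% | 24% | 32% |

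**3. Would the baseline-comparison rule catch it?** The plan does not define a baseline difference. If it means p<0.05 and half are maintained, the standard error of the difference is √(2 × 0.25/80) = 0.079 at 80 per arm and √(2 × 0.25/60) = 0.091 at 60. A 10-point difference then gives p=0.21 and p=0.27. The trigger is about 1.96 × 0.079 = 15.5 points, or 1.96 × 0.091 = 17.9 points. Most imbalances of 10 points or more would go unadjusted, even if status were among the variables compared.

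**4. What adjustment gains.** If status explains a share R² of the outcome variance, the residual SD is √(1 − R²), and power follows from d/√(1 − R²) at 60 per arm, two-sided 0.05:

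| Assumed R² | d/√(1 − R²) | Power |
|---|---|---|
| 0 | 0.500 | 78% |
| 5% | 0.513 | 80% |
| 10% | 0.527 | 82% |
| 20% | 0.559 | 86% |

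**5. What those R² values mean.** With half maintained and a gap of g SD between the groups, R² = 0.25g². So 5 to 20% corresponds to g = √(0.05/0.25) = 0.45 up to √(0.20/0.25) = 0.89. A 10-point imbalance then moves the treatment difference by 0.10 × 0.45 = 0.04 to 0.10 × 0.89 = 0.09 SD, against a design effect of 0.5. The documents give no estimate of g.

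**6. Which term does the work.** If baseline is one of the time points, a main effect of status absorbs only a difference in level. The expected difference is in course, so the status-by-time term is needed.

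**The case against.** The plan is not blind to this. It compares baseline opiate use, a partial proxy for status, and adjusts if the arms differ. Randomisation protects the contrast in expectation. Both points stand: a reader might infer that the factor is wholly uncontrolled or confounds the treatment effect, and the documents support neither. What remains is that test-then-adjust is weaker than prespecification and does not name status.

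A reader might also infer that Secondary Aim 1 certainly meets a baseline floor. The protocol says only that such patients are already taking buprenorphine, not that they are stable or abstinent, and criterion 3 would limit a floor if it binds everyone.

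Nor can the loss be sized from clinic numbers. The 166 + 115 = 281 existing clinic patients, times the 46/99 PTSD rate among new admissions, gives about 131. Set against 46 new patients a year, that is 74% of a one-year pool or 49% of a three-year pool. But this assumes no turnover, equal uptake and no new Newington admissions, and leaves out the PTSD clinics, advertising, community clinics and Bedford. Diluting d=0.5 by those shares gives power of about 28% (49% maintained) or 11% (74%), but only with a fixed SD and zero effect in maintained patients. If that group has no variance, power at 49% is 36-49% when the users' common change is 0 to 1 SD. Zero effect also ignores relapse prevention, which the protocol's rationale expects.

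Finally, restricting the main opioid test to baseline users is not a clear remedy. On the same shares it leaves about 31 or 16 per arm (49% or 28% power at d=0.5), drops relapse from the test and departs from intent-to-treat.

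**Conclusion.** The point holds as one of precision, chance imbalance and interpretability, not of bias. Newly inducted and existing buprenorphine patients are mixed, and entry status appears in neither the stratification nor the prespecified models. If half are maintained, an arm difference of at least 10 points has a 24 to 32% chance. Adjusting for status is worth roughly 2 to 8 points of power (78% to 80-86%) if it explains 5 to 20% of outcome variance. Both the share and the variance explained are assumptions. The size of any floor in opioid use cannot be derived from the documents; it depends on how criterion 3 is read. Stratification or adjustment would not remove such a floor, so the clarification and the supportive analyses below are needed as well. The contradiction between universal induction and skipped induction is in the text and rests on no assumption.

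**What to change.** 1. Prespecify buprenorphine status at entry (new induction or already taking) and status-by-time, plus baseline TLFB opioid use, as covariates in the PTSD and opioid-use models, and status in the retention comparison. Apply this to all randomised patients, replacing the test-then-adjust rule for these variables. In the opioid-use model, state whether the baseline month is a time point or a covariate; it should not be both.
2. Add status as a stratum for remaining randomisations, if practical. With concurrent medications this makes four cells.
3. Keep the intent-to-treat opioid-use test in all participants as the main analysis for Secondary Aim 1. Report the effect by status, and in those with any baseline use, as supportive analyses.
4. State whether criterion 3's urine requirement applies to patients already taking buprenorphine. Reconcile criterion 3, the Methods overview, the induction text under Standard Treatment and the Potential Risks statement with the rule on skipping induction, so that both sites admit the same population.

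The cost is one or two model terms using data known at entry, plus protocol and SAP wording. The covariate change can be made without altering any allocation already done, but should be fixed before results by arm are seen.
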